**BACKGROUND**

[figure not shown]
This protocol is supported by a NIMH award that is organized into two phases. The goals of the first (R61) and second (R33) phases are to demonstrate target engagement and then clinical effect by the therapeutic intervention, respectively. Specifically, the primary goal of the R61 phase is to employ multimodal imaging to explicitly test for the assumed DLPFC engagement (fMRI) and modulation of frontal gamma activity (EEG) by tDCS, investigate the optimization of tDCS application parameters, and confirm the tolerability of tDCS for schizophrenia patients, and will be the focus of this protocol. After confirming that this effect is driven by tDCS effects in a positive direction, the current strength that has the highest effect size and also meets >80% completion rate will be the one that is selected for the R33 phase, which will seek to demonstrate clinical effect by assessing clinical outcomes scales and observing improvements in cognitive control mediated by DLPFC and frontal gamma oscillation engagement.

A successful outcome of this study would provide tDCS the sound mechanistic, methodologic and clinical-relevance basis for more definitive testing in large-scale clinical trials as a highly innovative therapeutic intervention for cognitive impairments in schizophrenia.

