### Hypothesis

The primary hypothesis to be tested in this study is observing positive modulations in fMRI BOLD signals in the DLPFC and EEG frontal gamma oscillations during a cognitive control task following frontal tDCS modulation. We hypothesize tDCS application at 2.5 mA will show greatest engagement of DLPFC and frontal gamma oscillations and that 80% of subjects will complete the full tDCS protocol.

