## OVERVIEW OF STUDY DESIGN

We aim to investigate transcranial Direct Current Stimulation (tDCS) as a novel therapeutic for cognition in psychosis. We will recruit 100 early phase schizophrenia patients with cognitive control deficits. A range of current strengths will also be explored, ranging from 1.5 to 2.5 mA in 0.5 mA increments. Thus, the subjects will be divided into four groups of N=25 for each of the tDCS current strengths including a sham stimulation (placebo) group.

We will recruit equal numbers of female and male participants. Subjects will have less than five years of treatment history and currently be on stable doses of second-generation antipsychotic medications for at least one month. Antipsychotic exposure history will be fully assessed and converted into standardized equivalents. The total duration of this study will be approximately 2 weeks. However, the majority of the study will be within a one week period.

Table 1: Overview of Study Design								
Procedure	Screening	Day 1	Day 2	Day 3	Day 4	Day 5	Day 6	Week 1
Medical, Medication History, Demographics, Color-blind screening	X							
Urine Screen	X							
MRI Screening Form	X							
Clinical Assessments	X							
Cognitive Assessments	X							
fMRI		X						X
EEG		X						X
tDCS			X	X	X	X	X	
Tolerability Assessment			X	X	X	X	X	
Comprehension Assessment	X	X	X	X	X	X	X	X
Payment	\$40	\$75	\$10	\$10	\$10	\$10	\$10	\$75
Total								\$240

**Screening:** Participants who provide written informed consent will undergo screening procedures and a review of the study eligibility criteria. At this visit the participant will complete the initial screening process, which includes detailed demographic information (including medication and treatment information), diagnostic information using the M.I.N.I diagnostic neuropsychiatric interview (M.I.N.I 7.0.2). Additionally, a cognitive assessment, MATRICS, will be conducted to assess level of cognitive functioning. Psychopathological ratings that are conducted include: the Brief Psychiatric Rating Scale (BPRS), the Scale for the Assessment of Positive Symptoms (SAPS), the Scale for the Assessment of Negative Symptoms (SANS) the 7-point Clinical Global Impression (CGI) Scale, the Global Assessment of Functioning (GAF). If participants meet the inclusion/exclusion criteria (see section Subject Population), participants continue to next visit.

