## **TREATMENT ALLOCATION AND BLINDING**

### **Randomization, Blinding and Tolerability Assessments**

Subjects will be randomly assigned to one of the three active tDCS (1.5 mA, 2.0 mA or 2.5 mA) or sham groups (N=25/group), under the constraint of group-level demographic and cognitive status matching. For robust blinding, we will coordinate three different teams of experimenters, responsible for 1) clinical/neuropsychological status evaluations; 2) tDCS application; and 3) EEG/fMRI recording and data analysis. Critical to our third aim, the second team will be responsible for assessing tolerability during the stimulation and general adherence to the stimulation sessions. We will employ a “triple-blind design” in the following manner to minimize unintended biases/confounds: randomized group assignment; automatic, computer control of the stimulator according to the encrypted subject’s group; de-identified data analysis.

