### **STATISTICAL METHODS**

**Primary Objective:** Dependent measures will be task condition-related differences in fMRI BOLD activation as measured through GLM and EEG oscillatory activity in the gamma band as analytically estimated by complex wavelet transformation. Group and time point differences will first be assessed with omnibus tests instantiated through the general linear model (e.g., repeated measures ANOVA) to determine the presence and direction of potential effects. Effects equivalent to  $f \geq .16$  will be targeted. To determine the efficacy of the treatment conditions, we plan to conduct post-hoc comparisons of the post- minus pre-test differences between each active stimulation group and the sham stimulation group, as well as within each group between the post- and pre-test measures. The behavioral context of these changes will also be assessed by the Inc-Con difference in accuracy and reaction time in an analogous manner to fMRI and EEG measures.

**Secondary Objective:** Initial analytical targets will be identified concurrent with Aim 1. Polynomial trend analyses will be used to determine the dose-response curve to tDCS. To assess the degree of efficacy of each treatment, Cohen's  $d_z$ , a measure of effect size similar to Cohen's  $d$  which also accounts for the covariance between measures, will be calculated within each group based on the difference between control-related activations from the pre- and post-test assessments with an ideal target of  $d_z = .534$  for fMRI BOLD activation and  $d_z = .687$  for EEG gamma synchrony (i.e., half the observed distance between patient and control measures based on preliminary data). As an exploratory analysis, we will also make use of the structural MRIs to create individualized head models of current strength in the DLPFC. Since the current strength, distribution and even polarity can vary considerably as a function of individual physiology and anatomy, such comparisons between the predictive value of the tDCS device's current output vs. the modeled current strength in relation to the fMRI

and EEG measures will be invaluable in informing future investigations of personalized treatment protocols and tDCS tolerability/safety.

**Tertiary Objective:** A target completion rate of 80% serves as our benchmark for assessing feasibility. No analysis is required - this benchmark will simply serve as the required threshold for starting the R33 phase.

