**R61 to R33 Phase Transition Criteria:** Our 'Go/No-go' strategy for this transition will require an effect size of tDCS to be  $f \geq .16$  for both DLPFC BOLD signal and frontal EEG gamma activity. After confirming that this effect is driven by tDCS effects in a positive direction, the current strength that has the highest effect size *and* also meets >80% completion rate will be the one that is selected for the R33 phase.

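### Do the 80% and >80% completion thresholds give two conflicting Go/No-go rules for R33?

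*Combined protocol and SAP*

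**What the plan says.** Four places bear on the completion threshold.

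- STATISTICAL METHODS, Tertiary Objective: "A target completion rate of 80% serves as our benchmark for assessing feasibility", and "this benchmark will simply serve as the required threshold for starting the R33 phase". It gives no inequality, does not say whether the rate is per current strength or overall, and names no denominator. It also states that no analysis is needed, so the observed rate is used as it stands.
- STATISTICAL METHODS, R61 to R33 Phase Transition Criteria: both target measures must reach the stated effect size in a positive direction. The strength with the largest effect that "also meets >80% completion rate will be the one that is selected for the R33 phase" is then taken forward.
- BACKGROUND repeats that rule: "the current strength that has the highest effect size and also meets >80% completion rate".
- Hypothesis: "80% of subjects will complete the full tDCS protocol". This is an expectation, not a decision rule.

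On arm size, OVERVIEW OF STUDY DESIGN says "the subjects will be divided into four groups of N=25 for each of the tDCS current strengths", sham included. The section on randomization and blinding gives the same 25 per group.

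**The concern.** In ordinary use a threshold of 80% is met at 80%, whereas a requirement of more than 80% is not. The planned arm size makes the difference attainable, because four fifths of 25 is a whole number. Both statements concern entry to R33, both are current text, and neither is expressly placed above the other.

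If they were rival rules, a strength with exactly 20 completers could be called eligible or ineligible, and the choice might be made after completion and effect sizes were known. Since the observed rate is applied with no test or interval, the wording is the whole rule. A second uncertainty is the level: the Hypothesis speaks of subjects in general and the Tertiary Objective names no strength, so a rate pooled over all participants is a conceivable reading.

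**Working it through.** **Inputs.** 100 participants in four groups, so 100/4 = 25 per arm, which agrees with the stated group size. The thresholds are 80% (Tertiary Objective) and >80% (transition criteria, BACKGROUND). The documents give no expected completion rate for each arm, so true rates of 80%, 85% and 90% are assumed below.

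**Step 1: where the wordings part.** At least 80% of n needs the smallest whole number x with x ≥ 0.8n; more than 80% needs the smallest x with x > 0.8n.

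| n | 0.8n | at least 80% | more than 80% |
|---|---|---|---|
| 24 | 19.2 | 20 | 20 |
| 25 | 20.0 | 20 | 21 |
| 26 | 20.8 | 21 | 21 |

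The counts differ only when n is a multiple of 5, and then by one completer. The planned 25 is such a case; 24 or 26 is not.

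**Step 2: whether the decision parts.** R33 carries forward one selected strength. Selection is described only in BACKGROUND and the transition criteria, and both demand more than 80%. The Tertiary Objective calls its figure required, which makes it a necessary condition. Read per strength as at least 80%:

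| Completers of 25 | Tertiary Objective | Transition criteria | Strength can be selected |
|---|---|---|---|
| 19 (76%) | not met | not met | no |
| 20 (80%) | met | not met | no |
| 21 (84%) | met | met | yes |

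In every row the last column equals the transition-criteria column. Both statements can hold together, and jointly they require 21 of 25.

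**Step 3: the size if they were rival rules.** Let X be Binomial(25, p), with three independent active arms sharing p. The chance that no active strength qualifies is (1 − P(X ≥ 21))³ under more than 80% and (1 − P(X ≥ 20))³ under at least 80%.

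| p | P(X ≥ 20) | P(X ≥ 21) | none qualifies, >80% | none qualifies, ≥80% |
|---|---|---|---|---|
| 0.80 | 0.6167 | 0.4207 | 0.5793³ = 19.4% | 0.3833³ = 5.6% |
| 0.85 | 0.8385 | 0.6821 | 0.3179³ = 3.2% | 0.1615³ = 0.4% |
| 0.90 | 0.9666 | 0.9020 | 0.0980³ = 0.09% | 0.0334³ = 0.004% |

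The last column depends on a selection rule of at least 80% per strength, which no section states. The contrast is therefore hypothetical.

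**Step 4: the pooled reading.** Suppose the Tertiary Objective meant at least 80 of all 100, sham included. The figures below come from the exact convolution of four Binomial(25, p) arms.

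- The pooled rate is met while every active arm has 20 or fewer: 2.3%, 1.3% and 0.08% at p = 0.80, 0.85 and 0.90. No strength could then be selected, so the answer is still no-go.
- The pooled rate fails while at least one active arm has 21 or more: 27.0%, 4.7% and 0.06%. This would change the answer only if the pooled rate were an additional requirement.

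**The case for a change.** The strongest case on the other side is that a Go/No-go criterion should be free of loose ends. The Tertiary Objective calls its own figure the requirement for starting R33, and nothing says that the next paragraph overrides it. The planned arm size falls exactly on the boundary: at a true rate of 80%, the study's own reference value, an arm has exactly 20 completers with probability 0.6167 − 0.4207 = 19.6%. If the Tertiary Objective is a separate overall requirement, it could block a strength that passes, and aligning the wording would cost almost nothing.

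Some of this stands. The wording does differ, and the level and denominator are unstated. The denominator can matter at the margin: 20 of 25 fails more than 80%, while 20 of 24 (83.3%) passes. A reader must therefore settle who is counted, and all those randomised to the strength is the conventional choice.

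The charge of conflicting decisions does not stand. An overriding clause is unnecessary when both conditions can be satisfied together and the stricter one decides. The blocking scenario needs three things the text does not supply: pooling, inclusion of sham, and a requirement that both rates hold. The paragraph headed as the transition criteria sets out the Go/No-go conditions and lists no overall rate. The 27.0% also assumes a true rate exactly at the threshold, and it is 4.7% at 85%.

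**Conclusion.** The concern does not call for a change. The two wordings differ by one completer at 25 per arm and by none at 24 or 26. Following the transition criteria as written, the per-strength decision is the same whichever way the 80% is read: a strength with 20 of 25 is not selected and one with 21 of 25 passes on completion. Neither inequality is shown to be wrong, and making the Tertiary Objective repeat the stricter wording would alter no per-strength decision.

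This rests on two readings: that the transition criteria mean what they say about selection, and that the Tertiary Objective states a necessary condition per strength, or a feasibility benchmark, and not an extra pooled requirement. The level and denominator remain unstated. Analysts can handle that by applying the rule to each strength among those randomised and reporting the overall rate beside it. The definition of completion is less open, since the Hypothesis, Poor Adherence and Stopping Rules text all refer to finishing the tDCS course. All of this concerns only the completion condition of the phase transition. The effect-size condition, the endpoint analyses and participant safety are unaffected.

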## REGULATORY ETHICS COMPLIANCE

### Investigator Responsibilities

The investigator is responsible for ensuring the study is performed in accordance with the protocol, current ICH guidelines on Good Clinical Practice, and applicable regulatory requirements. During the study the investigator will send the following documents and updates to the Baylor College of Medicine Institutional Review Board for their review and approval, where appropriate:

- a) Protocol amendments (excluding the ones that are purely administrative, with no consequences for subjects, data or study contact)
- b) Revision(s) to ICF and any other written materials to be provided to subjects.
- c) Revisions to compensation for study-related injuries or payment to subjects for participation in the study, if applicable.
- d) Reports of adverse events that are serious, unlisted/unexpected, and associated with the study protocol.
- e) Deviations from or changes to the protocol to eliminate immediate hazards to the subjects.
- f) Any other requirements of the IRB.

At the end of the study, the investigator will notify the IRB about the study completion.

### Informed Consent

Each subject must give written consent according to local requirements after the nature of the study has been fully explained. The ICF will be signed before performance of any study-related activity. The ICF that is used must be approved by the reviewing IRB and be in a language that the subject can read and understand. The informed consent should be in accordance with principles with current ICH and GCP guidelines and applicable regulatory requirements. Before enrollment in the study, the investigator or an authorized member of the study-site personnel must explain to potential subjects the aims, methods, reasonably anticipated benefits, and potential hazards of the study, and any discomfort participation in the study may entail. Subjects will be informed that their participation is voluntary and that they may withdraw consent to participate at any time. They will be informed that choosing not to participate will not affect the care the subject will receive for the treatment of his or her disease.

The subject will be given sufficient time to read the ICF and the opportunity to ask any questions. After having obtained written consent, a copy of the ICF will be provided to the participant.

IRB approval will be sought from Baylor College of Medicine Institutional Review Board. Privacy and confidentiality will be maintained with a special number to be used to identify the subject in the study and only the investigator and his research staff will know their name.

### **Privacy of Personal Data**

The clinical information obtained from subjects will be part of their study records and maintained at BCM in a facility with adequate safeguards for the protection of confidentiality. The research data will be collected and recorded using only arbitrary study IDs. All data will be kept in a secure area. Only the members of the research group will have access to the data files or to the master list for the codes (linking log form attached). For publication purposes, the patients will be designated only by codes. Our research team is in compliance with all HIPAA privacy guidelines. In summary, the potential risks for participants in this study will be minimized by careful medical and psychiatric evaluations and procedures, regular monitoring of subjects' clinical status, careful screening of subjects before the EEG and MRI scans and defined procedures for maintaining confidentiality.

### **Quality Control and Assurance**

The study will be monitored by a Data Safety Monitoring Board (DSMB). The DSMB will independently review the protocol and consent documents, AEs, and outcome data as needed, for the proposed study. The DSMB will evaluate issues related to subject safety and the adequacy and integrity of accumulated data. The DSMB will meet once for every 20 subjects who have completed the study to review the study. Data reports will be prepared by [name] study coordinator to support the work of the DSMB.

The study coordinator will create tables for the DSMB to review. The tables will include enrollment, demographic information by treatment arm, abnormal laboratory results, SAEs, and missing data. After each meeting, the DSMB will issue a memo documenting any action items for the team. Copies will be provided to the Baylor IRB upon request.

[name] lab will conduct routine (bimonthly) reviews of consistency, reliability and accuracy of data collected for any paper records. Similar checks for any data in electronic form will also be conducted but in an automated fashion (e.g checking for accurate time/date stamps, file sizes etc.).

**Stopping Rules:** Participants must complete the 5 consecutive days of tDCS treatment within a maximum of 6 consecutive days. Appointments will be scheduled for 5 consecutive days however, if a participant misses an appointment we will only allow one day to be rescheduled. If the 5 sessions are not completed within the 6 days allotted the participant will be withdrawn from the study.

### **Confidentiality and Assured Data Transfer and Safety Monitoring**

Data collected at the MEDVAMC are to be used in a multi-site study that combines MEDVAMC data with BCM data. Furthermore, the data will be disclosed to BCM, which is the coordinating center, where the data will be combined and analyzed for this study. Below are further details on the coordination of data between sites.

All physical research data that is collected at the Michael E. DeBakey VA Medical Center will be kept on site ([name]). Data collected at the Baylor College of Medicine Greenpark I site will also be kept at that respective site ([name]). The research data collected at the MEDVAMC will be in a locked file cabinet in a locked room at the MEDVAMC campus ([name]). Data collected at the Baylor College of Medicine Greenpark I site will also be locked in a file cabinet in a locked room ([name]). All de-identified study data will be available only to personnel involved in the study through the use of access privileges and passwords.

During the course of the study, trained research staff supervised directly by the PI will monitor participants. The study coordinator and data analysts will meet weekly with the PIs (and/or appropriate co-investigators), to review data and study issues including data analysis, recruitment, and confidentiality. In the event of an adverse event or breaches in confidentiality, the research staff will immediately communicate to the PI. This information will be communicated immediately to the IRB. If changes to the protocol become necessary to insure continued confidentiality measures, or to ensure the level of risk associated with this study, the IRB will be notified immediately, and these modifications will be addressed for review and approval as quickly as possible. Except for adverse events or modifications, a summary of study progress will be forwarded to the IRB with the annual renewal application. There is no conflict of interest on the part of any of the key personnel associated with this study. Information about this study can also be found at [clinicaltrials.gov](http://clinicaltrials.gov).

An Accounting and Disclosure (AOD) will be created and maintained for any disclosure of individually identifiable information (III) outside the VA. The manual spreadsheet will include the date of the disclosure and the name and address of person or agency to which the disclosure was made.

## **Publication Plan**

Final analysis and preparation of manuscripts will occur during months 23-24 of Phases 1 and 2 respectively.
